16.1 Primary Endpoint Analyses

The primary endpoint in the efficacy expansion cohorts is the confirmed BOR according to RECIST 1.1 and as adjudicated by an IERC, defined as the best response obtained among all tumor assessment visits after start of study treatment until documented disease progression (taking into account the requirement for confirmation). Only tumor assessments performed before the start of any further anti-cancer treatment will be considered in the assessment of BOR.

For the gastric / GEJ cancer, HNSCC, and ovarian cancer efficacy expansion cohorts, the primary analysis of the BOR by IERC will be conducted in the FAS, defined as all treated subjects. The number and proportion of BOR (defined as CR + PR) will be tabulated. The ORR will be determined as the proportion of subjects with a confirmed BOR of PR or CR. An exact binomial test will be performed at a 1-sided alpha level of 0.025. The primary analysis is planned 6 months after start of treatment of the last subject in the given cohort. Interim analyses will be conducted after 60% of the subjects in the given cohort have been followed up for 13 weeks. Analyses are considered positive if the lower limit of the 95% confidence interval exceed 10%. Confidence intervals will be constructed using the Clopper-Pearson method.

For the urothelial carcinoma efficacy expansion cohort, the analysis of the BOR by IERC will be conducted in the PD-L1 positive FAS followed by the FAS. The number and proportion of BOR (defined as CR + PR) will be tabulated. The ORR will be determined as the proportion of subjects with a confirmed BOR of PR or CR. An exact binomial test will be performed in the PD-L1 positive FAS and in the FAS to determine whether the null hypothesis of an $ORR \leq 10\%$ can be rejected at the 1-sided alpha level of 0.025. Interim analyses will be conducted at 4 and 6 months after the first dose date of last subject of the 109 subjects enrolled in the urothelial carcinoma efficacy expansion cohort prior to Protocol Amendment 13. Respective cut-off dates are 18Jan2016 and 19Mar2016. Analyses are considered positive if the lower limit of the 95% CI of the confirmed BOR exceeds 10%. Confidence intervals will be constructed using the Clopper-Pearson method.

The tumor response will be based on the IERC assessment of overall response at each time point. Details of determination of tumor response are provided in Imaging Review charter document. A separate Imaging Data Management Plan and Data Transfer Plan will be created to summarize the details of the data structure and data delivery schedule of IERC assessment results.

The following are the requirements for confirmation of CR or PR or of minimum SD duration:

- CR or PR needs to be confirmed at a subsequent tumor assessment, preferably at the regularly scheduled 6-week assessment interval, but no sooner than 4 weeks after the initial documentation of CR or PR.
- The minimum duration for a BOR of SD is defined as at least 37 days after start of study treatment accounting for permitted deviations from the tumor assessment visit schedule.

Table 6 summarizes the derivation rules for the BOR when confirmation from subsequent assessment is needed (1). It is reasonable to consider a subject with time point response of PR-SD-

PR, PR-NE-PR or CR-NE-CR as a confirmed response as long as the second CR or PR is ≥ 28 days away from the first time point.

Table 6 Best overall response when confirmation of CR/PR required

Initial overall response	Subsequent overall response	Confirmed time point overall response
CR	CR	CR provided subsequent CR is ≥ 28 days away from the first time point
CR	PR	SD provided minimum criteria for SD duration met; otherwise, PD
CR	SD	SD provided minimum criteria for SD duration met; otherwise, PD
CR	PD	SD provided minimum criteria for SD duration met; otherwise, PD
CR	NE	SD provided minimum criteria for SD duration met, otherwise, NE
PR	CR	PR provided subsequent CR is ≥ 28 days away from the first time point
PR	PR	PR provided subsequent PR is ≥ 28 days away from the first time point
PR	SD	SD
PR	PD	SD provided minimum criteria for SD duration met, otherwise, PD
PR	NE	SD provided minimum criteria for SD duration met, otherwise, NE
SD	Any	SD provided minimum criteria for SD duration met, otherwise, NE
PD	Any	PD
NE	NE	NE

CR = complete response, PR = partial response, SD = stable disease, PD = progressive disease, and NE = Not evaluable.
If a subject only has a response value of NE or the only response value is SD and is within 36 days of the first dose date the best response will be NE.

In addition, the unadjusted 95% CIs of the ORR will also be calculated with the Clopper-Pearson method at the interim and primary analyses in order to provide comparable results based on the FAS and subgroup analysis. The number and percentage of subjects with BOR of CR, PR, SD, Non-CR/Non-PD, PD, and NE will be tabulated.

16.2 Secondary Endpoint Analyses

Clinical efficacy parameters will be analyzed descriptively in the FAS, and, in addition, for the urothelial carcinoma efficacy expansion cohort, in the PD-L1 positive FAS. Pooling of data from subjects with at least 6 months follow-up period in the urothelial carcinoma efficacy and secondary cohorts may be considered to enhance precision of estimates if data is sufficiently homogeneous. The following efficacy endpoints will be considered: The confirmed and unconfirmed BOR, per RECIST 1.1, as adjudicated by an IERC and per investigator assessment; irBOR according to modified irRC per investigator assessment, DR, TTR, and PFS time according to RECIST 1.1 criteria per IERC and investigator assessment; DR, TTR, and irPFS time according to irRC criteria

per investigator assessment; OS time. Subgroup analyses specified in Section 16.2.6 and summary of demographics will also be presented for pooled population.

The percent change in target lesions from baseline will be derived as:

- $((\text{Sum of target lesions at week XX} - \text{sum of target lesions at baseline}) / \text{sum of target lesions at baseline}) * 100\%$

The maximum reduction in target lesions from baseline will be derived across all the post-baseline assessments as:

- Minimum of $((\text{sum of target lesions at week XX} - \text{sum of target lesions at baseline}) / \text{sum of target lesions at baseline}) * 100\%$

The tumor shrinkage will be calculated based on investigator assessment for all the expansion cohorts and, in addition, based on IERC data for efficacy expansion cohorts and the urothelial carcinoma secondary cohort. The percent change from baseline in target lesions per time point as well as other relevant information will be presented in a data listing. The percent change from baseline in target lesions as well as the first occurrence of new lesion and subject off treatment overall and by PD-L1 expression status will be displayed against time point (weeks) in spider plots. The maximum reduction from baseline in the sum of target lesion diameters overall and by PD-L1 expression status will be presented per subject in waterfall plots. The PD-L1 expression status will be displayed using different colors or line styles in the plots. The time point of a tumor assessment per investigator is defined as the earliest scan date of the respective visit.

BOR per investigator assessment will be determined according to RECIST 1.1 for all the expansion cohorts. CR/PR will be confirmed per Table 5 in [Section 16.1](#). irBOR is defined as the best result obtained among all tumor assessment visits from baseline until immune related disease progression (i.e., confirmed irPD), and will be determined according to modified irRC per investigator assessment, taking confirmation requirements into account as detailed below. Only tumor assessments performed before the start of any further anti-cancer treatment will be considered in the assessment of BOR/irBOR. In addition to the confirmed BOR/irBOR, the unconfirmed BOR will be derived for the interim and/or primary analyses. The date of unconfirmed BOR / confirmed BOR / irBOR will be the date of the best result that is first observed, or first confirmed if the confirmation is required. In case of different dates of scans within the same tumor assessment visit, the earliest scan date should be used as the date of tumor assessment.

Subjects with a BOR of NE will be summarized by reason for having NE status and displayed in a listing with relevant data. The following reasons will be used:

- No post-baseline assessments
- All post-baseline assessments have overall response NE
- New anticancer therapy started before first post-baseline assessment
- SD of insufficient duration (<6 weeks after start date without further evaluable tumor assessment)
- PD too late (>12 weeks after start date)

A contingency table will be created to compare the following tumor assessment results between IERC and investigators:

- BOR (NE / PD / (Non-CR/Non-PD) / SD / CR / PR / CR+PR)
- Disease Progression (No event / PD / Death)

For irBOR, the response of immune-related complete response (irCR), immune-related partial response (irPR), and irPD need to be confirmed by a second, consecutive assessment at least 4 weeks apart as described in Table 7 (1, 2). It is reasonable to consider a subject with time point response of irPR-irSD-irPR, irPR-NE-irPR or irCR-NE-irCR as a confirmed response as long as the second irCR or irPR is more than 28 days away from the first time point. irPD is also considered to be confirmed if the following event occurs:

- If subject is assessed with time point response of irPD-NE-irPD as long as the second irPD is more than 28 days away from the first time point; or
- If subject dies within 84 days after the initial observation of irPD; or
- If subject receives subsequent anti-cancer drug therapy within 84 days after the initial observation of irPD; or
- If subject experiences clinical deterioration as assessed by investigator and recorded as reason for treatment discontinuation prior to or within 84 days after the assessment of irPD.

In case a subject with a confirmed CR relapses within 1 year after stopping treatment, one re-initiation of treatment is allowed according to Protocol. If the subject has irPD assessed at the same visit as the PD prior to the initiation of treatment, the irPD will be considered as confirmed. Immune-related stable disease (irSD) duration is required to be no less than 37 days from Day 1.

Table 7 Immune-related BOR when confirmation of irCR, irPR, irPD required

Initial overall response	Subsequent overall response	Confirmed time point overall response
irCR	irCR	irCR provided subsequent irCR is ≥ 28 days away from the first time point
irCR	irPR	irSD provided minimum criteria for irSD duration met; otherwise, irPD
irCR	irSD	irSD provided minimum criteria for irSD duration met; otherwise, irPD
irCR	irPD	irSD provided minimum criteria for irSD duration met; otherwise, irPD
irCR	NE	irSD provided minimum criteria for irSD duration met, otherwise, NE
irPR	irCR	irPR provided subsequent irCR is ≥ 28 days away from the first time point
irPR	irPR	irPR provided subsequent irPR is ≥ 28 days away from the first time point
irPR	irSD	irSD
irPR	irPD	irSD provided minimum criteria for irSD duration met, otherwise, irPD
irPR	NE	irSD provided minimum criteria for irSD duration met, otherwise, NE
irSD	Any	irSD provided minimum criteria for irSD duration met, otherwise, NE
irPD	irPD	irPD provided subsequent irPD is ≥ 28 days away from the first time point, death or take subsequent anti-cancer drug therapy within 84 days after the first time point, or clinical deterioration.

Initial overall response	Subsequent overall response	Confirmed time point overall response
irPD	Missing	irPD if subject dies or takes subsequent anti-cancer drug therapy within 84 days after the initial observation of irPD, or clinical deterioration, otherwise, NE
NE	NE	NE

irCR = immune-related complete response, irPR = immune related partial response, irSD = immune related stable disease, irPD = immune related progressive disease, and NE = Not evaluable.

If a subject only has a response value of NE or the only response value is irSD and is within 36 days of the first dose date the best response will be NE

In general, efficacy analyses on secondary endpoints will be performed as follows:

- Unconfirmed response at week 13 only applies to the interim analyses performed on the first 75 subjects for all the primary cohorts.
- Unconfirmed BOR and PFS per investigator assessment applies to all the interim analyses for all the expansion cohorts.
- Unconfirmed/confirmed BOR and PFS per IERC apply to the interim analyses for the efficacy expansion cohorts and the urothelial carcinoma secondary cohort if data is available.
- All the endpoints (unconfirmed/confirmed BOR, irBOR, PFS/irPFS, DR/immune-related DR, TTR, OS) per investigator assessment except for unconfirmed response at week 13 apply to primary analysis for all the expansion cohort. PFS, TTR and DR per IERC will also be analyzed for efficacy expansion cohort and the urothelial carcinoma secondary cohort if data is available.

The details will be provided in the Table, Listing, and Figure Shells document.

16.2.1 Objective Tumor Response According to RECIST 1.1 or Modified irRC (per investigator assessment)

Objective tumor response is defined as having a BOR assessment of unconfirmed/confirmed CR/PR, or having an irBOR assessment of irCR/irPR. Objective tumor response will be evaluated by ORR or immune-related objective response rate (irORR) for each cohort, defined as the number of subjects reached a best overall response of CR/PR (irCR/irPR) divided by the number of subjects in the FAS (PD-L1 positive FAS)/ EFF (PD-L1 positive EFF). Time to objective response will be calculated as:

$(\text{Date of the first documented objective response (PR or CR)} - \text{date of the first dose} + 1) / 7$ (weeks)

Two-sided 80% and 95% exact CIs for ORR or irORR will be estimated using Clopper-Pearson method for each cohort. Additionally, the number and percentage of subjects with BOR of CR, PR, SD, PD, and NE or irBOR of irCR, irPR, irSD, irPD, and NE will be tabulated.

These evaluations will be presented in data listings with detailed information collected per eCRF pages as well as BOR and irBOR for all the subjects from the FAS subjects. Time to response, time of progression, and duration of study treatment will be displayed in a bar chart for subjects with objective response.

16.2.2 Duration of Response According to RECIST 1.1 or Modified irRC

DR is measured from the time measurement criteria are first met for CR/PR or irCR/irPR (whichever is first recorded) until the first date that progressive disease or death within 84 days of last tumor assessment is objectively documented. The analysis of DR will be performed among the subjects who had unconfirmed/confirmed CR/PR or irCR/irPR.

DR will be censored in the following scenarios:

- Subjects who have not experienced an event (PD or death) will be right-censored on the date of their last evaluable tumor assessment.
- If death without previously documented PD is observed after more than 84 days (12 weeks) of last tumor assessment, subject will be right-censored at the date of the last evaluable tumor assessment.

$DR = (\text{date of PD or death/censoring} - \text{date of first documented objective response} + 1) / 30.4375$ (months).

The Kaplan-Meier method will be used to estimate parameters for duration of response. Kaplan-Meier estimates (product-limit estimates) will be presented together with a summary of associated statistics including corresponding two-sided 95% CIs. In particular, the proportion of duration of responses at 6 and 12 months will be estimated with corresponding two-sided 95% CIs. The CIs for the median will be calculated according to Brookmeyer and Crowley (4) and CIs for the survival function estimates at the above defined time points will be derived using the log-log transformation according to Kalbfleisch and Prentice (5) (CONFTYPE = loglog default option in SAS PROC LIFETEST). The estimate of the standard error will be computed using Greenwood's formula. A listing with pertinent information will be provided.

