7.1.4 Post-Treatment Safety Follow-Up

All subjects will have a subsequent visit scheduled 10 weeks after the last administration of avelumab. The visit will include the following full assessment of safety parameters (refer to [Appendix I](#)):

- Any treatment related AEs and concomitant medications will be documented, including further anti-cancer therapy.
- Vital signs and body weight will be measured.
- Physical examination will be performed.
- ECOG performance status will be assessed.
- 12-lead ECG will be assessed.
- Laboratory testing consisting of the following will be assessed:
 - hematology, hemostaseology, full serum chemistry, and full urinalysis
 - T4 and TSH levels
 - PK sample (any remaining sample may be used for ADA determination)
- A urine β -HCG pregnancy test (in women of child bearing potential) will be conducted.

After the End-of-Treatment visit only treatment-related AEs have to be documented until the Post-treatment Safety Follow-up visit. Subjects with a SAE ongoing at the post-treatment safety follow-up visit must be monitored and followed up by the investigator until stabilization or until the outcome is known, unless the subject is documented as “lost to follow up.”

Subjects without progressive disease according to RECIST 1.1 at the end-of-treatment visit will be followed up for radiographic disease progression (CT / MRI scans) every 12 weeks up to 1 year.

After the end-of-treatment visit, subjects will be followed quarterly (\pm 14 days) for survival (including assessment of any further tumor therapy). The survival follow-up will continue until 1 year after the last subject receives the last dose of avelumab.

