The assumption of an ORR of 27% in PD-L1 positive subjects in the urothelial carcinoma efficacy expansion cohort is supported by preliminary results of the urothelial carcinoma secondary expansion cohort.

In the given populations of refractory metastatic cancer patients, it is considered that superiority compared with an ORR of 10% may indicate clinical benefit if the observed responses are durable. The assumption of an ORR of 20% in an unselected population in gastric / GEJ cancer, HNSCC, and ovarian cancer is supported by results from clinical studies with anti-PD-1 / anti-PD-L1 agents.

The sample size of 150 for each of the 4 primary disease specific expansion cohorts has been chosen primarily to further explore the safety and efficacy of avelumab in specific indications, as well as in subgroups defined by PD-L1 tumor expression status, and to provide data to aid in future study design.

From an efficacy perspective, the sample size of 150 in each of the primary expansion cohorts will provide estimates and 95% Clopper-Pearson CIs for response rate of 10% (5.7%, 16.0%) in the case of 15 responders out of 150 subjects, and of 20% (13.9%, 27.3%) in the case of 30 responders out of 150 subjects.

Furthermore, the following can be said regarding the precision of estimated response rates in subjects that are positive for PD-L1 expression: For given proportions of PD-L1 positive subjects

in an expected range of 30 to 70% and given response rates in the subgroup of PD-L1 positive subjects in an expected range from 20 to 33%, the subgroup analysis 95% Clopper-Pearson CIs based on a total sample size of 150 will be as shown in [Table 8.1](#).

Table 8.1 95% Confidence Intervals of Estimated Response Rates

	Response rate in PD-L1 positive subjects	
	20%	33.3%
Proportion and absolute number of PD-L1 positive subjects (N=150)	95% CI	95% CI
30% (45)	(9.6%, 34.6%)	(20.0%, 49.0%)
50% (75)	(11.6%, 30.8%)	(22.9%, 45.2%)
70% (105)	(12.8%, 28.9%)	(24.4%, 43.2%)

CI: confidence interval; PD-L1: Programmed death ligand 1.

The sample size of 120 in the ovarian cancer secondary expansion cohort will provide estimates and 95% Clopper-Pearson CIs for response rate of 10% (5.3%, 16.8%) in the case of 12 responders out of 120 subjects, and of 20% (13.3%, 28.3%) in the case of 24 responders out of 120 subjects.

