16.2.3 Progression-Free Survival According to RECIST 1.1 or Modified irRC

PFS time is defined as the time from first administration of study treatment until date of the first documentation of PD or death by any cause (whichever occurs first), when death occurs within 84 days of last tumor assessment or first administration of study treatment (whichever is later).

PFS will be censored in the following scenarios:

- Subjects who do not have any post-baseline tumor assessment, or do not have a baseline tumor assessment, and die (when applicable) more than 84 days after initial avelumab dose will be right-censored on the date of first dose of study treatment.
- Subjects who have not experienced an event (PD or death) will be right-censored on the date of their last evaluable tumor assessment.
- If death without previously documented PD is observed after more than 84 days of last evaluable tumor assessment, subject will be right-censored at the date of the last evaluable tumor assessment.

$PFS = (\text{date of PD or death/censoring} - \text{date of the first dose} + 1)/30.4375$ (months).

The analysis of PFS will be performed with a Kaplan-Meier method with the same approach as for duration of response described in Section 16.2.2. Kaplan-Meier estimates (product-limit estimates) will be presented together with a summary of associated statistics including corresponding two-sided 95% CIs. In particular, the proportion of PFS at 3, 6, and 12 months will be estimated with corresponding two-sided 95% CIs. Kaplan-Meier plots of PFS time and listing of PFS will be provided as well.

Frequency (number and percentage) of patients with each event type (PD or death) and censoring reasons will be presented. Censoring reasons are as follows:

- Ongoing in the study without an event (PD or death)
- No baseline assessment
- No adequate post-baseline assessments
- No documented PD and death more than 84 days after last evaluable tumor assessment.

The PFS time or censoring time and the reasons for censoring will also be presented in a patient listing.

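### Best response stops at new anti-cancer therapy, but duration of response, PFS and maximum tumour shrinkage run on through it, with no reason given and no sensitivity analysis

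*SAP*

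**What the plan says.** **Best response.** On the primary endpoint, SAP 16.1 says: "Only tumor assessments performed before the start of any further anti-cancer treatment will be considered in the assessment of BOR". SAP 16.2 applies the same rule to the investigator-assessed and immune-related versions: "Only tumor assessments performed before the start of any further anti-cancer treatment will be considered in the assessment of BOR/irBOR".

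**DR and PFS.** SAP 16.2.2 lists two censoring scenarios for DR. One is "Subjects who have not experienced an event (PD or death) will be right-censored on the date of their last evaluable tumor assessment". The other covers late deaths: "If death without previously documented PD is observed after more than 84 days (12 weeks) of last tumor assessment", the subject is censored at the last evaluable scan. SAP 16.2.3 uses the same two for PFS and adds one for subjects lacking a baseline or any post-baseline scan. None of them mentions new therapy. Protocol 8.3.2, which defines both endpoints, has no such rule either.

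**Shrinkage.** SAP 16.2: "The maximum reduction in target lesions from baseline will be derived across all the post-baseline assessments".

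**Scanning after treatment.** Under Protocol 7.1.4, subjects without RECIST progression at the end-of-treatment visit "will be followed up for radiographic disease progression (CT / MRI scans) every 12 weeks up to 1 year". The start of another therapy does not end this, and Protocol 6.13 leaves care after withdrawal from trial treatment to subject and physician.

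**Role of DR.** Protocol 8.1 explains the 10% null rate by saying that "superiority compared with an ORR of 10% may indicate clinical benefit if the observed responses are durable".

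**The concern.** ORR and the DR that qualifies it are measured over different windows. A responder who stops avelumab without progression and starts another drug has a best response from avelumab alone, but a DR and a PFS time that keep running on the other drug. In a single-arm trial no control group offsets this, so the 6- and 12-month DR proportions planned in SAP 16.2.2 may not describe durability on avelumab.

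The SAP does not state that it chose to follow subjects through later therapy. Its other rules point the opposite way. Section 11 removes data after avelumab re-initiation from the efficacy analyses (overall survival excepted), and it ends the on-treatment period the day before subsequent anti-cancer drug therapy. Renewed avelumab is therefore excluded from DR and PFS while a different drug is not. The sensitivity analyses in 16.2.7 concern only tumour response in the full versus the efficacy analysis set.

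**Working it through.** **1. The plan's own figures.** No stated figure depends on the DR or PFS windows. The stated ORR power reproduces for a single look at a 10% null, 20% true rate and one-sided 0.025. With N=150, success needs 24 responders (exact alpha 0.0143, power 91.1%, stated about 91%). With N=100 it needs 17 (exact alpha 0.0206, power 80.8%, stated about 80%). These do not move, because best response is already cut at new therapy.

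**2. Windows side by side.**

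| Measure | Place | Ends at new therapy? |
|---|---|---|
| BOR, irBOR | SAP 16.1, 16.2 | Yes |
| DR | SAP 16.2.2, Protocol 8.3.2 | No |
| PFS | SAP 16.2.3, Protocol 8.3.2 | No |
| Maximum reduction | SAP 16.2 | No |

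**3. Can it happen?** Yes. Protocol 3.4 reports 80 of 480 expansion subjects (16.7%) off treatment permanently for an adverse event by 5 November 2014. How many were progression-free or later switched is not given.

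**4. Shrinkage.** Let A be the scans before new therapy and B those after it. The minimum percent change over A and B together is never greater than the minimum over A alone. Adding B leaves the apparent best reduction unchanged or makes it deeper.

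**5. One subject (illustration).** PR at Day 43, last scan before the switch at Day 127, clean scan at month 13 (about Day 396). With the SAP formula, DR is (127 − 43 + 1)/30.4375 = 2.8 months if cut at the switch, and (396 − 43 + 1)/30.4375 = 11.6 months if carried through. Both are censored times.

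**6. Effect on 12-month DR (assumptions only).** Let λ = ln 2/m be the hazard of progression or death on avelumab, where m is the median in months. Let f be the share of responders whose first transition is a switch, so the switch hazard is s = λf/(1 − f). After the switch the hazard is hλ. With k = λ + s − hλ, the carried-through proportion event-free at t is

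S(t) = exp(−(λ+s)t) + s·exp(−hλt)·(1 − exp(−kt))/k.

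If switching is non-informative, censoring at the switch recovers exp(−λt).

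Example with m = 12, f = 0.30, h = 0.5, t = 12: λ = 0.0578, s = 0.0248, k = 0.0536, so S = 0.3715 + 0.1549 = 0.526, against 0.500 when censored.

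| m | f | h=0.33 | h=0.5 | h=1.0 | h=1.5 |
|---|---|---|---|---|---|
| 12 | 5% | 50.5% | 50.4% | 50.0% | 49.7% |
| 12 | 10% | 51.0% | 50.7% | 50.0% | 49.4% |
| 12 | 20% | 52.2% | 51.6% | 50.0% | 48.7% |
| 12 | 30% | 53.7% | 52.6% | 50.0% | 47.9% |
| 6 | 5% | 26.2% | 25.8% | 25.0% | 24.5% |
| 6 | 30% | 33.1% | 30.5% | 25.0% | 21.6% |

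Over these scenarios the difference from the censored value runs from −3.4 points (21.6 − 25.0) to +8.1 points (33.1 − 25.0).

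**7. Censoring reasons.** SAP 16.2.3 tabulates four for PFS: ongoing without an event, no baseline scan, no adequate post-baseline scan, and late death. The OS list in 16.2.4 separates withdrawal of consent and loss to follow-up; the PFS list does not. Neither the DR nor the PFS output would show how many times run through new therapy.

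**The case against.** **Carry-through is a recognised choice.** Following subjects through later therapy is a treatment-policy approach, and it matches Protocol 8.3.2. The cut for best response is what the SAP added: Protocol 8.5.2.2 runs best response to documented progression. This stands, and it argues against replacing the main DR and PFS analyses.

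**Censoring at new therapy has its own bias.** Protocol 5.5.2 foresees stopping avelumab when treatment failure calls urgently for another drug, and Protocol 7.3 when the subject clinically deteriorates. Subjects who switch that way before RECIST progression are failing. Censoring them could raise the Kaplan-Meier estimate, whereas the present rule keeps their later progression or death. This stands too, and the model in the working does not cover it.

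**Some information is planned.** The primary analysis adds a table of later anti-cancer treatment (SAP 14.3). Spider plots mark when subjects go off treatment (16.2), and a bar chart shows treatment duration for responders (16.2.1). Under the immune-related criteria, later drug therapy within 84 days confirms an earlier irPD. None of these shows what DR or PFS would be without the new-therapy period.

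**Stakes.** Protocol 8.1 sets no DR threshold, and Protocol 8.5.1 treats everything beyond the primary endpoint as exploratory. That is correct and limits the importance.

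**A reader might infer that subjects who switch, withdraw or are lost can appear only as ongoing in the PFS table.** That goes too far. Those without a usable post-baseline scan, and late deaths, have their own categories, and withdrawal and loss are counted in disposition (SAP 12.1).

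**Conclusion.** The mismatch is real and unexplained. For maximum shrinkage the bias has one direction: another drug's effect can deepen the plotted reduction and can never make it shallower.

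For DR and PFS the direction is open. A reader might infer that the present rule credits later disease control to avelumab. The documents do not support that, because progression and death after a switch also count as events. The estimate rises only if later therapy controls disease better than continuing without a switch. Protocol 3.5.5.1 and 3.5.5.4 describe the ovarian and gastric populations as having few or no established options left. The single-subject contrast of 11.6 against 2.8 months likewise does not show an inflated median, since a censored time of 2.8 months does not by itself shorten a Kaplan-Meier estimate.

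The range of −3.4 to +8.1 points in 12-month DR rests on assumed medians of 6 and 12 months, 5% to 30% switching, post-switch hazard ratios of 0.33 to 1.5, constant hazards and non-informative switching. None of these values comes from the documents. The primary ORR test, its alpha and its power are unaffected. This is an inexpensive improvement to secondary analyses and does not threaten the trial's main result.

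**What to change.** 1. In SAP 16.2, limit percent change and maximum reduction in target lesions to scans before the start of further anti-cancer therapy, the same cut that best response has.
2. Keep DR and PFS as the protocol defines them, and say that this is a deliberate choice. In 16.2.2 and 16.2.3 add a sensitivity analysis that censors at the last evaluable scan before new anti-cancer therapy. Report both versions, including the 6- and 12-month DR proportions. State whether later radiotherapy and surgery count as new therapy, since SAP 14.3 collects all three.
3. Tabulate how many DR and PFS times run through new therapy, and how many are censored at it in the sensitivity analysis. In the PFS reasons, separate withdrawal of consent and loss to follow-up from ongoing, as the OS list already does.

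The cost is SAP wording, some programming and extra output. Later treatment is already collected (SAP 14.3), and SAP 11 already handles partial start dates for subsequent drug therapy. Censoring at new therapy may be informative when subjects switch because they are failing, which is why both versions should be shown.
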